Unsupervised clustering techniques will also be used to cluster the subjects according to the similarity of their gene expression profiles (before and after treatment), independently of clinical diagnosis or other investigator-designated categories. To limit noise and increase the strength of our findings, only genes with ample variability are used for cluster analysis (criterion values for variability will be determined empirically). The Hierarchical Ordered Partition and Collapsing Hybrid (HOPAH) (27) algorithm for building a hierarchical tree of clusters will be used for our cluster analysis. The number of clusters will be determined by Median Split Silhouette (MSS) (62) and biological consideration. The non-parametric bootstrap technique will be used for validating the HOPAH clusters. The clustering analyses will be assessed by using HOPAH package software in Bioconductor (27). Clustering of the

subjects based on gene expression would suggest a distinct, common underlying biological basis for disease in these subjects. Such an outcome could be a significant start in achieving one of our goals – a biology-based, rather than a clinical outcome-based classification of TZD response. Comparison of subject symptoms and clinical outcomes within- and across subject clusters based defined by gene expression profiling could be indicative of differences among subjects in response of TZD treatment.

Because the regulation of gene expression is a dynamic process, it is also important to identify and characterize changes in gene expression in response of TZD treatment among subject subgroups defined by expression profiling. Storey, et al. (73) proposed a general statistical method that identifies genes differentially expressed over time among different classes and have developed freely available software called EDGE. It is applicable to detecting differences in the behavior of expression in response to TZD treatment among different subgroups of the subjects. In addition to the pre-post comparison for each subgroup described above, the EDGE program will be used to identify genes that show significant differential expression in response to TZD treatment among different subjects.

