We will then analyze the biological significance of the genes which are identified by the above analyses, using GenMAPP (15) (Gene MicroArray Pathway Profiler) and MAPPFinder (19). GenMAPP facilitates the viewing and analysis of gene expression data in the context of biological pathways. The pathways are represented in a special file format called a "MAPP". The MAPPs are independent of the gene expression data and can be used to group genes and view data by any organizing principle. MAPPFinder uses GenMAPP and the Gene Ontology (GO) database (<http://www.geneontology.org>) to identify biological trends in gene expression data. MAPPFinder can use the terminology and organizing principles of the GO database, or user-defined MAPPs. The three organizing principles of GO are "molecular function", "biological process" and "cellular component", which are attributes of gene products. Each of these terms has sub-terms ("children") organized in a tree-like structure. The terms are assigned independently, such that each gene can fall into all three groups. Our analysis will identify (on the basis of z-score and permuted p-value) molecular functions, biological processes or cellular components that are potentially influential in the subjects in regard to TZD treatment. Based on microarray and functional genomic analyses and Q-RT-PCR validation, we will select 100 candidate genes that influence TZD response for Aim 2 study.

Software. The statistical software packages SAS, Bioconduct and R (27) are the primary tools for most statistical analysis. SAS software, which is installed on our computers, is a combination of programs originally designed to perform statistical analysis of data. R is a free software environment for statistical computing and graphics. Bioconductor is an open source and open development software project for the analysis and comprehension of genomic data. These approaches as well as others that emerge during the course of this project in the continually evolving field of microarray analysis will be utilized to process the data obtained in our microarray experiments.

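### EDGE p-values and FDR across expression-defined clusters are not valid, because the clusters are built from the data being tested; the size depends on what is clustered, which the plan leaves open

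*Combined protocol and SAP*

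**What the plan says.** All of this is in section D.2.f (Laboratory methods) under Aim 1, mainly in the Statistical approach.

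- **Forming the groups.** "Unsupervised clustering techniques will also be used to cluster the subjects according to the similarity of their gene expression profiles (before and after treatment"). Before clustering, "only genes with ample variability are used for cluster analysis"; the cut-off is to be set empirically. "The number of clusters will be determined by Median Split Silhouette (MSS) (62) and biological consideration". The clusters are checked by a non-parametric bootstrap.
- **Testing the groups.** The plan then turns to "changes in gene expression in response of TZD treatment among subject subgroups defined by expression profiling". Of EDGE it says: "It is applicable to detecting differences in the behavior of expression in response to TZD treatment among different subgroups of the subjects". The stated output is inferential: "the EDGE program will be used to identify genes that show significant differential expression in response to TZD treatment among different subjects". That sentence ends with subjects rather than subgroups, but the two sentences before it show that subgroups are meant.
- **Error rate.** Earlier in the same text, FDRs of 1-5% are anticipated for each analysis of differential expression.
- **Use of the result.** Pathway tools are applied to "the genes which are identified by the above analyses". The 100 candidate genes are then chosen from the microarray and functional genomic analyses and Q-RT-PCR validation. The Q-RT-PCR uses the same RNA samples as the arrays.

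The plan describes no sample split, hold-out set, selective-inference correction or null reference that repeats the clustering.

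**The concern.** A test of whether expression change differs between groups takes the group labels as given independently of the expression data. Here an algorithm chooses the labels to separate subjects on those same arrays. Even in one homogeneous population, some genes will differ between the resulting clusters more than chance labels would allow. The p-values then lose their nominal meaning, as does any FDR computed from them.

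At stake is the credibility of one gene list. Genes may appear on it because they drove the clustering, for instance through tissue composition or batch, without any link to insulin-sensitivity response. Since the list is one of several inputs to pathway analysis and to the choice of the 100 candidates, it may add such genes there.

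**Working it through.** **Is there a figure to reproduce?** No. The 1-5% FDR is a target, and no error rate or power is given for the cluster-then-EDGE step. The check is therefore a simulation under a known null.

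**Inputs from the documents:** 75 subjects with paired pre and post arrays; subjects clustered on expression; change in expression tested across clusters; FDR up to 5%.

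**Assumed inputs (not in the documents):** 2,000 genes; 2 or 3 clusters; Ward clustering as a stand-in for HOPACH; gene correlation through 0, 20 or 5 co-expression modules with loading 0.5 (0.5² = 0.25 of a unit-variance gene's variance is shared); stable within-subject share ρ of 0.2, 0.5 or 0.8.

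**Test.** For each gene, d = post − pre. Across k clusters,

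F = [Σ n_c(d̄_c − d̄)² / (k − 1)] / [ΣΣ(d_i − d̄_c)² / (75 − k)],

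with 1 and 73 degrees of freedom for k = 2, or 2 and 72 for k = 3. With two time points this is a group-by-time test. Benjamini-Hochberg (BH) at 5% follows. A valid test gives p<0.05 in 5% of genes, here 0.05 × 2,000 = 100.

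**Why the clustered quantity matters.** If pre (a) and post (b) levels are clustered together, the squared distance between two subjects is |Δa|² + |Δb|² = ½(|Δ(a+b)|² + |Δ(b−a)|²). With unit variances, Var(b−a) = 2(1−ρ) and Var(a+b) = 2(1+ρ). The change therefore supplies a share (1−ρ)/2 of the distance: 0.40, 0.25 and 0.10 for ρ = 0.2, 0.5 and 0.8. If the change itself is clustered, the share is 1. The circularity is present in every case but much weaker in the last.

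**Results with no subgroups present (Ward, 2-3 clusters):**

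| Clustered on | Genes | Share with p<0.05 | Genes passing BH 5% |
|---|---|---|---|
| Change | independent | 7-8% | at least one in 18-33% of runs |
| Change | 20 modules | 16-20% | at least one in 88-95% of runs |
| Change | 5 modules | 33-48% | about 380-680 on average |
| Pre and post levels | all settings | about 5-16% | 0-37 on average |
| Labels unrelated to expression | control | about 5% | – |

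In counts out of 2,000, 16-20% is 320-400 genes, 33-48% is 660-960, and 5-16% is 100-320, against 100 expected. For levels, ρ = 0.8 gives 5-6%. The top of the range occurs with 5 modules and ρ = 0.2, where repeat runs gave 14-18%.

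**Cross-check with k-means (4,000 genes).**
- Clustering on the change gave 11-12%, 19-21% and 26-32% when 10 common factors carried 10%, 20% and 30% of gene variance.
- Clustering on levels gave 5.1-10.4% with 10 factors, 5.1-5.7% at ρ = 0.8, and 22-27% in the most adverse setting (5 factors, ρ = 0.2).
- Independent genes gave 5.1-5.9%.
- Unrelated labels gave 4.7-5.3%, and some gene passed BH in 48 of 1,180 runs (48/1,180 = 4.1%).

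**Do the plan's safeguards repair it?** MSS chooses the number of clusters from the same data. A gene-resampling bootstrap reproduced cluster assignments 98-99.6% of the time although no subgroups existed, so cluster stability in that sense does not validate the later tests. Q-RT-PCR on the same RNA confirms the measurement, not the subgroup difference.

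**The case against.** The strongest reply has four parts.

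1. **Levels, not change.** The natural reading of clustering profiles before and after treatment is that levels are clustered, while EDGE tests the response. A reader might infer that the clusters are chosen to maximise the tested differences and that hundreds of genes will be falsely declared. That holds only if the change itself is clustered, which the plan does not say. This part stands and governs the size. It does not remove the problem, because levels still contain the change.

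2. **Planned filters were not simulated.** The plan gives a fold-change criterion (example above 1.5) alongside the p-value, and MSS and the bootstrap bear on the clusters. With a 1.5-fold between-cluster difference required and an assumed SD of change of 0.3-0.5 log2, clustering on the change left 0-17 genes with 20 modules and 0-119 with 5. This stands as a limit on the numbers. A filter shortens the list but does not make its p-values valid.

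3. **Candidate selection rests mainly on clinical response.** A reader might infer that true candidates are displaced. The documents do not support that. The study overview (D.1), the Aim 1c plan (D.2.e) and the regression score in D.2.f tie selection to correlation with clinical response. The closing selection sentence names no EDGE p-value, and no displacement was quantified.

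4. **The step is exploratory.** The plan itself urges caution with microarray results, and expression clustering plays no part in the Aim 3 tests in DPP and TRIPOD. This stands and limits the consequence. The plan nonetheless claims significance for this list.

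**Conclusion.** The step is wrong as written: EDGE p-values and the anticipated 1-5% FDR are not valid across clusters formed from the same expression data, and nothing in the plan corrects for this.

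The size is uncertain. It ranges from close to nominal (levels clustered, profiles mostly stable within subject) to a third or more of genes at p<0.05 (change clustered, strongly correlated genes). It rests on assumed gene correlation, assumed within-subject stability, and Ward or k-means clustering in place of HOPACH. MSS, EDGE itself and the fold-change criterion were not simulated. Correlated genes are the relevant case, since co-regulated pathways are the plan's own premise.

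The harm is confined to this gene list, its stated FDR and what it may add to pathway analysis and the candidate pool. A reader might extend it to the primary insulin-sensitivity endpoint or to the Aim 3 associations in DPP and TRIPOD; neither uses these clusters. Comparing clinical outcomes across clusters, already planned, is not circular in this way.

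**What to change.** In the Statistical approach (D.2.f):

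- State what is clustered: pre levels, post levels, both, or the change.
- Run EDGE on groups not built from the tested expression data, such as thirds of the insulin-sensitivity response. Clusters from the other tissue are not a clean substitute, because both tissues come from the same subjects and may share batch effects.
- Label any EDGE list across expression-defined clusters as descriptive, and do not use its p-values or FDR in pathway analysis or in choosing the 100 candidates.
- Keep the planned comparison of clinical outcomes across clusters as the inferential use of the clusters.

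The cost is analysis wording only, with no new subjects, samples or assays. The downside is that one exploratory gene list becomes descriptive.

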 - a. Identify the baseline factors (e.g., age, gender, body mass index, etc.) that are predictive of TZD response to the measured traits.
 - b. Determine if the response of the primary trait (i.e., insulin sensitivity) to TZDs is correlated with the response of each of the secondary traits to TZDs.
 - c. Perform cDNA microarray analysis of muscle and fat before and after 3 months of rosiglitazone therapy to identify the genes and their corresponding pathways that are correlated to TZD response.
 - d. Perform quantitative real-time PCR to accurately quantify changes observed in the microarray analysis and to study expression of other genes of interest.
2. Define genes whose regulation correlates to TZD response. One-hundred of these TZD-response candidate genes will be extensively studied by:
 - a. Identifying common sequence variants through DNA sequencing and *in silico* SNP discovery.
 - b. Validating these SNPs and defining allele frequencies through genotype analysis of approximately 2000 SNPs in the 100 candidate genes in DNA samples from Caucasian and African American subjects.
3. Identify the SNPs and haplotypes in these 100 candidate genes that influence TZD response by performing association analysis in (1) the 75 subjects recruited for this study, (2) a subset of 597 individuals from the Diabetes Prevention Program study who were treated with the TZD,

troglitazone, and (3) 97 gestational diabetic Mexican American women who were treated with troglitazone in TRIPOD (and more recently with pioglitazone in PIPOD).

In summary, this project will seek to determine the genetic underpinnings of inter-individual variation in TZD response. Since TZDs are agonist for the nuclear receptor, PPAR γ , we will use a functional genomics approach to identify the molecular phenotype of TZD response from which candidate genes will be selected and studied in several populations. This proposal combines powerful functional genomics and high-throughput genetic approaches in a unique and innovative fashion to study physiologically well-characterized subjects in whom a controlled TZD intervention is performed.

B. BACKGROUND AND SIGNIFICANCE

1. Thiazolidinediones (TZDs), a Novel Class of Insulin Sensitizers

a. *PPAR γ and TZD mechanism of action*

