correlated to TZD response will be defined as candidate genes and will be pursued using state-of-the-art molecular genetic approaches to define all common sequence variation and haplotype structure of the gene. We will then genotype these SNPs in our subjects to determine if these SNPs or haplotypes associate with TZD response. Although the 75 subjects we plan to recruit for this study will provide very rich phenotype and microarray information for defining TZD response and for selecting candidate genes to study, they will not be particularly powerful to discern the effect of specific gene variants on clinical response to TZDs.

However, they may be useful in discerning associations of gene variants with mRNA levels encoded by that gene (or within the same regulatory pathway). Thus, in the next stage of our study, we will take advantage of established collaborations with investigators of large prospective studies which involved a TZD intervention and for which relevant response traits have been collected, the DPP Study, and the TRIPOD Study (now continued as PIPOD).

[figure not shown]

Fig. 9. Timeline of the study

High throughput genotyping of 1536 SNPs in 100 candidate genes will be performed in these cohorts and association of SNPs and haplotypes with TZD response will be examined. It is our hope that in a subset of these 100 candidate genes we will find consistent evidence for a role in TZD response, e.g., altered mRNA levels in those with the variant SNP/haplotype and association with TZD response in both populations.

2. **Specific Aim 1. Defining interindividual variability in TZD response**

a. *Subject recruitment and screening*

Seventy-five subjects will be recruited for this study from the following sources:

- A large database belonging to the Division comprising over 500 subjects recruited at health fairs. These subjects have provided basic health information, given blood for genotyping, and indicated that we may contact them to inform them about future genetic studies. Additionally, some subjects have had oral glucose tests. We have previously successfully recruited subjects from this collection. This collection will also allow rapid identification of potential volunteers for our study if the focus should later change to a particular genotype or clinical profile.

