We will validate the SNPs identified by sequencing and/or in silico SNP discovery by genotyping a subsample of 96 individuals (48 European Caucasians and 48 African Americans) selected also from our DNA repository. We anticipate that on average, we will have identified 20 SNPs per gene, requiring us to genotype \approx 2,000 SNPs/person (100 genes \times 20 SNPs/gene). Allele frequencies of SNPs and linkage disequilibrium (LD) between intragenic SNPs will be calculated. This information will be used to choose haplotype-tagging SNPs for genotype analysis in the larger sample. With allele frequency and linkage disequilibrium information, we will be able to eliminate some SNPs from subsequent analysis. For example, SNPs with allele frequencies < 5% or SNPs in high LD (e.g., $r^2 > 0.7$) with other SNPs will not be genotyped in the larger cohort. We will use algorithms to select haplotype-tagging SNPs to maximize the likelihood that we have captured most or all of the sequence variation. Haplotype-tagging SNPs (ht-SNPs) will be genotyped in three different population groups as described in the following section. The Illumina platform will be used for this large-scale genotyping effort, which will be performed at the Broad Institute of Harvard and MIT (see Letter from [name]).

4. Specific Aim 3. Association Analysis of Candidate Genes with TZD Response in Three Populations

We will genotype the htSNPs identified in Specific Aim 2 in three separate populations who have undergone a TZD intervention. Approximately 1,500 htSNPs from 100 genes will be genotyped in: (1) 75 subjects recruited for this study; (2) 597 troglitazone-treated individuals from the Diabetes Prevention Program, or DPP; and (3) 97 gestational diabetic Hispanic women who were treated with troglitazone (and more recently pioglitazone) from the TRIPOD/PIPOD study.

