In each population separately, we will compare mean insulin sensitivity according to genotype using analysis of variance. We will include age and sex in the analysis as covariates. In additional models, we will add multiple genotypes from the same or related pathways and test their potential interaction effects in a multiplicative fashion. Prior to analysis, we will perform a series of routine quality control checks on the genotype data that will include a repeatability analysis of a panel of 5% duplicate samples, and chi-square tests to assess compliance of the genotype distributions with Hardy-Weinberg Equilibrium. These procedures are routinely carried out in our laboratory. The primary analysis will be to determine if there is a dose response effect of genotype on the outcome. This analysis is conducted by assigning codes of 0, 1, or 2 to the genotype, with the value of the code reflecting the number of (minor) alleles. In addition, we will also carry out secondary analyses of the dominant and recessive genetic models to evaluate the effects of the respective homozygotes on TZD response.

a. *Haplotype-disease association analysis*

Haplotypes may potentially provide more information about an unobserved causal variant than single SNPs because of the increased resolution of multiple SNPs considered jointly to tease out the unobserved ancestral haplotype background on which mutation arose and which is shared among affected individuals. We plan to use Helix Tree, a commercially available software package designed for managing and analyzing data from large-scale genome-wide association studies, for our haplotype analysis.

The haplotype trend regression analysis in Helix Tree regresses the response variable using the estimated haplotype probabilities as the regression matrix, thereby properly incorporating the uncertainty in individual haplotype assignment inherent in population-based data. We will compute permutation-derived empirical significance levels for each candidate gene to eliminate bias due to incorrect distributional assumptions.

b. *Population stratification*

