One potential pitfall of association studies in population-based samples is false-positive signals resulting from population stratification. We will use an Illumina panel of 278 ancestry informative markers from the HumanHap 550K chip (Illumina; San Diego, CA) to account for potential effects of population stratification in our analyses either by adjusting the variance of the statistic or by adjusting the populations (88, 89). We attempt to eliminate false positives by assigning higher priority to signals that are replicated in multiple populations either at the same SNP, same haplotype block or same gene. We recognize that these methods represent global adjustments based on genome-wide averages of admixture, thus do not provide information about the chromosomal region containing SNPs of interest. However, newer methods are beginning to appear that attempt to define the ancestral blocks to potentially allow for local admixture adjustment in case-control analyses (90). We plan to evaluate new methods as they become available and integrate those that will add power to our analyses.

c. *Power calculation for the candidate gene analyses*

We estimated the effect sizes we could reasonably expect to detect at 80% power in these three samples. The calculations were made across a range of allele frequencies, and for sample sizes of 75, 97, and 585, in the current study, TRIPOD, and the Diabetes Prevention Program (DPP), respectively. For purposes of these calculations, we further assumed a dominant genetic model in which mean TZD response levels were to be compared between two genotype groups (e.g., AA vs. Aa/aa). The effect sizes are parameterized to reflect the difference between the group means, expressed in terms of the

standard deviation units. By convention, differences between groups of 0.8 SD, 0.5 SD and 0.2 SD are considered large, medium, and small effects, respectively.

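### Aim 3 sets haplotype significance gene by gene, with no formal adjustment over the 100 genes and no quantified replication rule

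*Combined protocol and SAP*

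**What the plan says.** Aim 3 (section A) sets the goal: "Identify the SNPs and haplotypes in these 100 candidate genes that influence TZD response by performing association analysis". Section D.4 gives the scale. "Approximately 1,500 htSNPs from 100 genes will be genotyped in" the current study (75 subjects), DPP (597) and TRIPOD/PIPOD (97). The single-SNP analysis, which is the primary one, is run cohort by cohort: "In each population separately, we will compare mean insulin sensitivity according to genotype using analysis of variance".

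For haplotypes, section D.4.a plans a trend regression and then the gene-wise permutation: "We will compute permutation-derived empirical significance levels for each candidate gene to eliminate bias due to incorrect distributional assumptions". The stated purpose is to guard against a wrong reference distribution. Multiplicity is not mentioned.

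Two other places bear on false positives. Section D.4.b describes "assigning higher priority to signals that are replicated in multiple populations either at the same SNP, same haplotype block or same gene" as an attempt to remove them. Section D.1 expresses the hope that "in a subset of these 100 candidate genes we will find consistent evidence for a role in TZD response", giving as an example altered mRNA together with association in both outside populations. Neither place fixes a threshold, a number of cohorts or a direction.

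Formal multiplicity control appears only in the microarray part of section D.2.f, which anticipates a false discovery rate of 1–5% for differential expression.

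**The concern.** A permutation test done one gene at a time protects the error rate of that gene only. Aim 3 will look at 100 such results in each of three cohorts and intends to identify which genes matter. Without an adjustment over the 100 genes, or a replication rule with known error, a reader of the results cannot tell how many of the nominally significant genes chance alone would produce.

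The plan treats the same problem formally at the expression step but not at the association step, which is the one meant to identify the variants that influence response.

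**Working it through.** **Inputs from the plan.** 100 genes, about 1,500 htSNPs and three cohorts (section D.4). Power figures: 80% or higher for 0.3 SD in DPP and for 0.7 SD with n = 75 and n = 97, at minor allele frequencies (MAF) of 0.1–0.5 under a dominant two-group model (section D.4.c). The DPP sample size is 585 in one paragraph of D.4.c and 597 in the next; the ranges below cover both.

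**Assumed, because section D.4 does not state it.** Two-sided 0.05 per test, with a range of 0.01–0.10.

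**Step 1: which level does the plan's power imply?** Carrier fraction c = 1 − (1 − MAF)²; noncentrality = d × √(n c (1 − c)); noncentral t with n − 2 degrees of freedom.

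- Example: DPP, n = 585, MAF 0.1. c = 0.19, so the noncentrality is 0.3 × √(585 × 0.19 × 0.81) = 2.85. Power is 81% at 0.05 and 26% at 0.0005.
- DPP at 0.3 SD, MAF 0.1–0.5: 81–96% at 0.05, which reproduces the plan's figure; 26–57% at 0.05/100 = 0.0005, which does not.
- n = 97 at 0.7 SD: 76–93% at 0.05, below 80% only at MAF 0.1.
- n = 75 at 0.7 SD: 65% at MAF 0.1, 82–85% at MAF 0.2–0.4 and 74% at MAF 0.5, so the plan's range is only partly reproduced.

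The stated power therefore fits an unadjusted level of about 0.05. It concerns a single-variant comparison, not the haplotype regression, but it is the only evidence of the level intended.

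**Step 2: one cohort, all 100 genes null.**

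- Expected nominally significant genes: 100 × 0.05 = 5 (binomial 95% range 1–10). It is 1 at 0.01 and 10 at 0.10. With 90 null genes it is 90 × 0.05 = 4.5.
- Chance of at least one, with independent genes: 1 − 0.95^100 = 99.4%.

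**Step 3: 0.05 reached in at least two of three cohorts.** Per null gene: 3 × 0.05² × 0.95 + 0.05³ = 0.00725.

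- Expected: 100 × 0.00725 = 0.725.
- Chance of at least one: 1 − (1 − 0.00725)^100 = 52%.
- At 0.01: 0.03 expected and a 3% chance. At 0.10: 2.8 expected and a 94% chance.

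**Step 4: the looser same-gene criterion.** About 1,500/100 = 15 SNPs per gene. If any SNP at 0.05 counts and the SNPs are treated as independent (an upper bound), a null gene is hit in one cohort with probability 1 − 0.95^15 = 0.537. It is hit in at least two of three with probability 3 × 0.537² × 0.463 + 0.537³ ≈ 0.55, or up to about 55 of 100 null genes.

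**Step 5: the primary single-SNP tests.** 1,500 × 0.05 = 75 nominally significant null SNPs per cohort, before the dominant and recessive models.

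**Step 6: after adjustment.** Bonferroni at 0.0005 leaves 100 × 0.0005 = 0.05 expected null genes per cohort and a family-wise error of 1 − 0.9995^100 = 4.9%. For MAF 0.1–0.5, the effect detectable with 80% power rises as follows:

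- DPP: from 0.23–0.30 to 0.36–0.46 SD.
- TRIPOD: from 0.58–0.73 to 0.91–1.16 SD.
- n = 75: from 0.66–0.84 to 1.04–1.33 SD.

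**The case against.** The strongest reply is that the plan does not accept single-cohort hits. Section D.4.b uses the cohorts to filter signals, and section D.4 describes the DPP work as replication. Section D.1 looks for association in both outside populations together with altered mRNA. Association in both outside populations at 0.05 would leave 100 × 0.05² = 0.25 null genes, and an independent mRNA criterion at 0.05 would leave 0.25 × 0.05 ≈ 0.01.

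Much of this stands. A reader might infer that about 5 null genes per cohort, 15 over three, will be declared response genes. The documents do not support that: no rule declares a gene from one cohort, and adding the cohorts together as extra chances of error inverts their role as a filter. Nor do they support saying that nothing guards against error across cohorts, since an informal safeguard exists. A claim that most named genes would be false has no basis either, because the fraction of true genes is unknown.

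The reply does not close the gap. Ranking replicated signals higher does not require replication before a gene is named, the wording in section D.1 is a hope, and a match at gene level can be very loose (step 4). A further fair point is that the haplotype test is not the primary analysis. The single-SNP tests have the larger count, so a remedy limited to haplotypes would be incomplete.

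**Conclusion.** The concern holds in this form: the haplotype significance level is set gene by gene, and section D.4 has neither a formal adjustment over the 100 genes nor a quantified replication rule. The size is about 5 nominally significant null genes per cohort, and about 0.7 reaching 0.05 in at least two of three cohorts, with a 52% chance of at least one.

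These figures rest on an assumed level of 0.05, which the stated DPP power supports but the plan does not state, and on all 100 genes being null, which makes 5 the ceiling at that level. The figure of 0.7 also needs independent cohorts, and the 52% needs independent genes. These are counts of nominal significance and of one possible replication reading. They do not predict how many genes the investigators would name.

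**What to change.** Before the association analysis:

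1. State the significance level and sidedness for Aim 3.
2. Within each cohort, use one common set of phenotype permutations for all 100 genes, which keeps the correlation between genes. Permute within ancestry strata, or permute ancestry-adjusted residuals: DPP is 55% Caucasian, 20% African-American and 16% Hispanic, so unrestricted shuffling is not valid where response and haplotype frequency both vary with ancestry. The markers planned in section D.4.b can supply the adjustment.
3. Beside each gene-wise p-value, report the value adjusted over the 100 genes, by min-p or by Benjamini–Hochberg at 5%. The latter is in line with the false discovery rate already anticipated in section D.2.f.
4. Apply the same kind of adjustment to the primary single-SNP tests over about 1,500 htSNPs.
5. Base any claim that a gene influences response on the adjusted value or on a fixed replication rule giving the number of cohorts, the threshold and the same direction of effect. DPP need not be the sole deciding cohort; that would displace the plan's cross-population replication.
6. In section D.4.c, state the alpha behind the present power figures and add the power at the adjusted level.

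The computing cost is small because permutations are already planned. The real cost is that fewer genes are named and power falls. In DPP at 0.3 SD it drops from 81–96% to about 26–57% at a Bonferroni level of 0.0005. Benjamini–Hochberg is generally less strict.
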